Rapid Acceleration for Diagnostics in Underserved Populations:
HOME TESTING
(RADx-UP HoT)

National Clinical Trial (NCT) Identified Number: Pending

Principal Investigators: [name] PhD MPH

Co-Investigators: [name], MSc

[name], DrPH, MPH

Sponsor: National Institute of Health

Funded by: National Institute of Health

Version Number: 2.0

19 May 2021

NCT04949243

Summary of Changes from Previous Version:

Affected Section(s)	Summary of Revisions Made	Rationale
Sections 1.1, 1.3, 4.1, 4.4, and 9.3	The at-home testing through the public health intervention will be 3 times a week for 4 weeks, instead of testing twice a week for 5 weeks.	More frequent testing is better suited to diagnosing asymptomatic/pre-symptomatic disease and prevent spread.
Section 1.3	Questionnaires/surveys will be administered only on baseline and weeks 1, 3, 5, 13, and 21. The Schedule of Events table has been updated to reflect these timepoints.	To reduce participant burden, questionnaires/surveys will only be administered on baseline and weeks, 1, 3, 5, 13, 21.
Section 1.3	The survey on knowledge of prevention approaches will be administered on weeks 5 and 21 instead of weeks 13 and 21.	Administering this questionnaire at week 5 and week 21 allows for a better perspective to see how the participant's knowledge has changed over time.
Section 1.3	The survey on feasibility of at-home testing has been removed from week 21. It will only be administered at week 5.	To reduce participant burden, this survey will only be asked once after the testing phase.
Section 1.3	Survey questions on Beliefs were added to the protocol for weeks 1, 5, and 21.	No new questions were added. The survey questions on Belief were already included in the questionnaire. It has now been specified as a new category of questions within the protocol.
Section 1.3	Anthropometrics (weight) was added as a measure to be taken at Baseline and week 5. Anthropometrics (height) was added as a measure to be taken at Baseline.	Socio-Demographic Data was already planned at Screening and Enrollment (now called Baseline). For additional clarity, anthropometrics have now been specified at Baseline. Height will be taken at Baseline. Since weight fluctuates, it will be taken at Baseline and week 5.

- United States (US) Code of Federal Regulations (CFR) applicable to clinical studies (45 CFR Part 46, 21 CFR Part 50, 21 CFR Part 56, 21 CFR Part 312, and/or 21 CFR Part 812)

National Institutes of Health (NIH)-funded investigators and study staff who are responsible for the conduct, management, or oversight of NIH-funded studies have completed Human Subjects Protection and ICH GCP Training.

The protocol, informed consent form(s), recruitment materials, and all participant materials will be submitted to the Institutional Review Board (IRB) for review and approval. Approval of both the protocol and the consent form must be obtained before any participant is enrolled. Any amendment to the protocol will require review and approval by the IRB before the changes are implemented to the study. In addition, all changes to the consent form will be IRB-approved; a determination will be made regarding whether a new consent needs to be obtained from participants who provided consent, using a previously approved consent form.

[figure not shown]
1 PROTOCOL SUMMARY

1.1 SYNOPSIS

Title:	Rapid Acceleration for Diagnostics in Underserved Populations: Home Testing (RADx-UP HoT)
Study Description:	This observational, cohort sub-study is embedded within a larger public health intervention that distributes at-home, self-administered, SARS-CoV-2 antigen testing kits to households within pre-selected communities through the CDC. Within this sub-study, we will evaluate the socio-behavioral mechanisms of SARS-CoV-2 community transmission, including social interactions, health behaviors, healthcare utilization, knowledge, disease burden, and feasibility of at-home testing. The study hypothesis is that positive at-home test results will be associated with altered self-reported social interactions and altered health behaviors compared to negative test results. Surveys and questionnaires will be completed by participants through the smartphone app or via call center phone calls according to the schedule of events. Questionnaires will collect data on demographic characteristics, medical history and health status, COVID testing and symptoms, social interactions, knowledge of prevention strategies, infection risk, and attitudes towards vaccines.
Objectives:	
Primary Objective:
 
• To assess self-reported social interactions following SARS CoV-2 at-home test result over the study period 
Secondary Objectives:
 
• To assess change in self-reported behaviors before and following SARS CoV-2 at-home test result over the study period• To assess the impact of at-home testing regimen on self-reported healthcare utilization for SARS CoV-2 treatment• To assess knowledge of SARS CoV-2 prevention approaches over the study period
Endpoints:	
Primary Endpoint:
 
• Proportion of respondents that report adhering to social distancing guidelines after a test result; comparison of proportion adherent after positive vs. negative test result 
Secondary Endpoints:
 
• Proportion of respondents that decide to act on precautionary behaviors after a test result• Point estimate and 95% confidence interval for each healthcare utilization measure and composite measure• Proportion of respondents that are knowledgeable of precautionary measures to prevent infection• Prevalence of positive test results with 95% confidence intervals
Study Population:	Adults and children > 8 years of age living within pre-identified communities participating in the public health intervention
Phase:	Not applicable

Description of Sites/Facilities Enrolling Participants:	This is a site-less, direct to participant study. Participants, up to 300,000, will be recruited for the sub-study within the communities participating in the larger public health intervention.
Description of Study Intervention:	Collection of survey data
Study Duration:	Total of up to 29 weeks, including up to 4 weeks of screening period and 25 weeks from the start of the study.
Participant Duration:	Up to 25 weeks: 4 weeks of active testing period and 17 weeks of follow-up. Last follow-up will be at week 21 with a 4 week window (up to week 25) to complete the surveys.

1.2 SCHEMA

1.3 SCHEDULE OF ACTIVITIES (SOA)

Study Period/Phase:	Screening & Enrollment Phase	Sub-study Questionnaires/Surveys							Comments & Notes	
		Testing Phase (Public Health Intervention)*				Follow-Up Phase				
Week:	Weeks-4 to 0	Baseline	Week 1	Week 2	Week 3	Week 4	Week 5	Week 13	Week 21	
Informed Consent and Assent when applicable		X								e-Consent via app or verbal consent via call center
Create mobile app account		X								For participants using the mobile app
Contact Information		X								
Socio-Demographic Data		X								
Medical History		X								
Anthropometrics – Weight		X				X				
Anthropometrics – Height		X								
Questionnaires										Questionnaires can be completed during the week after each test (regardless of the result).
• Social interactions		X	X		X		X	X	X	
• Behaviors										
• Symptoms										
• Healthcare utilization										
• Beliefs		X	X				X		X	
• Knowledge of prevention approaches							X		X	
• Feasibility of at-home testing							X			
Testing Adherence/Compliance reminders			X	X	X	X	X	X	X	

*The public health intervention (3 times a week at-home testing) does not require consent. Consent is only required for this sub-study which involves the questionnaires/surveys that are administered during the testing phase and follow-up phase.

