3 OBJECTIVES AND ENDPOINTS

Objectives	Outcome Measures	Endpoint
Primary		
1. To assess self-reported social interactions following SARS CoV-2 at-home test result over the study period	Assessments: self-reported data on social distancing, quarantine, social connectedness, healthcare utilization, well-being	Proportion of respondents that report adhering to social distancing guidelines after a test result for the entire study cohort and stratified by participant demographics (e.g., sex) of interest; comparison of proportion adherent after positive vs. negative test result
Secondary		
2. To assess change in self-reported behaviors before and following SARS CoV-2 at-home test result over the study period	Assessments: self-reported data on awareness of the issue, engagement, decisions to act, action, and maintenance	Proportion of respondents that decide to act on precautionary behaviors after a test result for the entire study cohort and stratified by participant demographics (e.g., gender) of interest
3. To assess the impact of at-home testing regimen on self-reported healthcare utilization for SARS CoV-2 treatment	Assessments: self-reported ED visits, hospitalizations, and ICU admission, for SARS CoV-2 evaluation or treatment	Point estimate and 95% confidence interval for each healthcare utilization measure and composite measure for the entire study cohort and stratified by participant demographics (e.g., gender) of interest
4. To assess knowledge of SARS CoV-2 prevention approaches over the study period	Assessments: self-reported data on perceptions and prevention of risks of contracting SARS CoV-2 infection	Proportion of respondents that are knowledgeable of precautionary measures to prevent infection for the entire study cohort and stratified by participant demographics (e.g., gender) of interest
5. Prevalence of positive test result for SARS CoV-2	Assessments: reported results of self-administered SARS CoV-2 antigen test	Prevalence of positive test results with 95% confidence intervals for the entire study cohort and stratified by participant demographic variables of interest

Exploratory		

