4.4 END OF STUDY DEFINITION

A participant is considered to have completed the study if he or she has completed the active testing period (at-home testing 3 times a week for 4 weeks) along with the questionnaires/surveys during those 4 weeks. Questionnaires/surveys will continue to be offered during the follow-up period (up to 17 weeks). Any amount of testing data and survey responses completed will be acceptable and analyzed.

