9.3 POPULATIONS FOR ANALYSES

The following populations are also defined:

Population	Description
Evaluable Population- Per protocol (PP)	Per protocol population will be those that report adhering to the following: 
 1. Self-administer the at-home test three times a week for 4 weeks 2. Complete questionnaires/surveys during the 4 week testing period
Modified per-protocol	Will include any participant who performed at least one at-home test
Second modified per-protocol	Will include any participant who completed at least one survey

All analyses will be conducted in the PP. A subset of analyses will be repeated in the modified PP populations as applicable.

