9.4 STATISTICAL ANALYSES

9.4.1 GENERAL APPROACH

The approach to analysis will be primarily descriptive. Demographics, questionnaire data, and testing results will be reviewed and summarized using graphical techniques and summary statistics. Where applicable, exact method confidence intervals will be computed around point estimates. Trends over time will be evaluated graphically. The proportion of participants adhering to social distancing guidelines after a positive vs. negative test result will be compared using tests of proportion clustered by participants with various levels of intra-participant correlation. Stratified analyses by test or week number will also be performed. We will explore the associations between positive test results and critical behavioral measures using mixed modeling techniques to account for the participant and

household correlations. Analyses will be conducted using SAS (SAS Institute, Cary NC) and R with R Studio (R-project).

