9.4.2 ANALYSIS OF THE PRIMARY EFFICACY ENDPOINT(S)

Point estimates with 95% confidence intervals will be reported. The analysis will be done for applicable study populations as described above, and stratified by participant demographics of interest (e.g., age, gender). There will be a comparison of the proportion of participants that report adhering to social distancing guidelines after positive vs. negative test result.

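### Does the primary comparison fail because the survey weeks do not line up with the three-times-weekly tests?

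*Combined protocol and SAP*

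**What the plan says.** Section 3 sets the primary objective as "To assess self-reported social interactions following SARS CoV-2 at-home test result over the study period". Section 9.4.2 states the contrast: "There will be a comparison of the proportion of participants that report adhering to social distancing guidelines after positive vs. negative test result". Neither place attaches an interval to the word after.

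The only text that ties survey timing to test timing is the comment in the Section 1.3 table: "Questionnaires can be completed during the week after each test (regardless of the result". The same table marks the social-interactions survey at Baseline and Weeks 1, 3, 5, 13 and 21.

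Section 9.3 describes the testing as "Self-administer the at-home test three times a week for 4 weeks" and, for the per-protocol set, also asks participants to "Complete questionnaires/surveys during the 4 week testing period". The synopsis (Section 1.1) splits participation into "4 weeks of active testing period and 17 weeks of follow-up". Section 4.4 adds that "Any amount of testing data and survey responses completed will be acceptable and analyzed".

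Section 9.4.1 says "Stratified analyses by test or week number will also be performed" and plans comparisons that allow for clustering within participants. Section 9 refers further analysis detail to a separate SAP, and Section 9.1 calls the analysis mainly descriptive, with an exploratory hypothesis.

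**The concern.** Read as a rule, the schedule note promises a survey in the week following every test, and the table beside it does not deliver that. Weeks 2 and 4 have no survey, and Weeks 13 and 21 come long after testing ends. A participant can have 12 results but only three survey responses close to them, so one response may follow several results, some positive and some negative. Nothing supplied says which result such a response belongs to, or whether the two late surveys enter the contrast.

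At stake is the meaning of the primary proportion. A one-week window, a two-week window, the latest result and any earlier positive each define a different group of responses after a positive. If the rule were chosen once the data had been seen, the choice could follow the result.

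**Working it through.** **Inputs from the documents.** Three tests a week for 4 weeks (Sections 4.4 and 9.3): 3 × 4 = 12 tests, the last no later than day 28. Near-test surveys in Week 1 (days 1–7), Week 3 (days 15–21) and Week 5 (days 29–35). Test days within the week are not given, and a completion window is stated only for Week 21.

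**The plan's own timeline.** 4 + 17 = 21 weeks, and a 4-week window gives 21 + 4 = 25. Both agree with the synopsis. Week 5 therefore belongs to follow-up.

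**Late surveys.** Week 13 starts on day 7 × 12 + 1 = 85, and 85 − 28 = 57 days. Week 21 starts on day 7 × 20 + 1 = 141, and 141 − 28 = 113 days. Neither lies in the week after a scheduled test.

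**How many of the 12 tests can have a survey in the following week?** The answer depends on assumptions the documents leave open.

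- *Next study week.* Only Week 2 (survey in Week 3) and Week 4 (survey in Week 5) qualify: 2 × 3 = 6.
- *Rolling 1–7 days, same three test days each week.* The seven days before any survey hold at most 3 tests, so the ceiling is 3 × 3 = 9. A Week 3 survey always has exactly 3 tests behind it; Weeks 1 and 5 have 0 to 3 each. The range is 3 to 9. Over all 35 choices of test days and 7 × 7 × 7 = 343 combinations of survey days, the mean is 6.0.
- *Rolling 1–7 days, spacing free.* Tests on days 1–3, 11–13, 15–17 and 22–24 with surveys on days 4, 18 and 29: 3 tests precede day 4 by 1–3 days, 6 precede day 18 by 1–7 days, and 3 precede day 29 by 5–7 days. Total 12.

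So 9 is a ceiling only for a fixed weekly pattern and a rolling window.

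**How far the choice of rule matters (constructed example; the documents give no positivity rate or test days).** Tests on days 1, 3 and 5 of each week, surveys on days 4, 18 and 32, and 12 participants, each with a run of three positives starting at a different test (cut off at the last test). That gives 12 × 3 = 36 responses.

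| Rule for after a positive | Weeks 1, 3, 5 | With Weeks 13, 21 (days 88, 144) added |
|---|---|---|
| Latest result positive | 8 | 14 |
| Any positive in prior 7 days | 10 | 10 |
| Any positive in prior 14 days | 16 | 16 |
| Any prior positive | 22 | 46 |

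Of the 10 responses under the 7-day rule, 5 also have a negative result in the same seven days. The late surveys supply 14 − 8 = 6 of 14 under the latest-result rule, 46 − 22 = 24 of 46 under any prior positive, and none under either window.

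**The case for a change.** The best case for a change is that a descriptive proportion still needs a defined denominator. Sections 9.4.1 and 9.4.2 commit to comparing positive with negative. In the example the group after a positive grows from 8 to 22 of 36 according to an unstated choice, nearly threefold. Stratifying by test presumes a link between response and result without defining it. If the schedule note is only a completion window, the supplied text contains no link at all. Writing the rule before data review would cost little.

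Much of this stands as description. No supplied passage pairs a response with a result, and mixed results within a week are to be expected. Three things limit its force.

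- The counts come from an invented cohort. They show that the definitions differ, not how far estimated adherence would move.
- No passage says the late surveys will be pooled with the near-test ones, and breakdown by week separates them.
- Several windows are defensible, each with a cost. A 7-day rule that also bars anyone with an earlier positive from the negative group would leave 36 − 10 − 14 = 12 of the 36 responses in neither group. A wider window mixes in later behaviour.

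The per-protocol survey requirement is not a fault here either. It decides who is analysed, not which of their responses are used.

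One practical caution remains. The audit trail in Section 10.1.9.1 records when data are entered. For participants interviewed by phone, that may be the interview date and not the test date.

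**Conclusion.** No change is called for. The apparent clash between note and table rests on reading a permissive comment as a promise of one survey per test. As a completion window it sits comfortably beside a survey schedule that was thinned on purpose to limit burden. The 6, 9 or 12 of 12 coverage figures depend on test spacing and on the meaning of the week after, neither of which the documents fix.

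The real residue is missing detail: how a response is assigned to one of up to 12 results, and where Weeks 13 and 21 belong. A competent analyst would settle this in the separate SAP, and the questionnaire items may already carry a recall period; neither was available for this review. The plan states no wrong rule, and any particular look-back window is a trade-off, not a correction.

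This judgement rests on the plan being mainly descriptive, on the breakdown by week being carried out, and on the pairing rule being set before the results are examined.

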2 INTRODUCTION

2.1 STUDY RATIONALE

The public health crisis of the COVID-19 pandemic continues to rage on across the US. Novel mitigation strategies and community level public health interventions are critical to stop the spread of this virus. One of these interventions is frequent, low-cost, rapid-result, at-home viral screening of asymptomatic and symptomatic individuals. The goal of frequent home testing is to identify SARS-CoV-2 index cases early, trigger isolation and quarantining precautions, and ultimately decrease community transmission.

The Centers for Disease Control, through coordination with public health departments, is conducting a public health intervention of frequent home testing, completed in a timeline needed to address the pressing need in high-risk communities. This intervention of home testing requires intentional engagement and a clear recognition of risk. Within pre-selected communities, CDC will distribute at-home, self-collect/self-test SARS-CoV-2 tests with instructions to complete regular testing irrespective of symptoms or exposure history. Previous at-home testing studies have generated inconclusive results, in part due to multiple factors including inadequate community engagement strategies to promote uptake and consistent testing in the target population as well as limited testing and prevention knowledge, attitudes and behavior.

This cohort sub-study in a subset of the population will explore the community and human behavior factors in response to at-home testing. Participants in the public health intervention who meet eligibility criteria will be invited to participate in the sub-study, consented, and asked to complete questionnaires aimed at evaluating self-reported social interactions, behaviors, and health system utilization in response to results from the at-home SARS CoV-2 antigen test. This sub-study will provide participant level behavioral information essential to understanding the relationship between large scale at-home testing and community transmission during the SARS-CoV-2 pandemic and relevant for implementation of public health interventions in future pandemics.

2.2 BACKGROUND

In the US, > 4 million people have been infected with the SARS-CoV-2 virus and >400,000 died. Infections and deaths, however, have disproportionately affected historically marginalized populations. Early in the pandemic the focus has been on testing to identify symptomatic individuals to reduce morbidity and mortality from infection. As public health measures have scaled up mitigation strategies are increasingly being considered to reduce community spread of infection. The availability of rapid tests for detecting SARS-CoV-2 presents opportunities for rapid, frequent and low-cost at-home testing in asymptomatic populations as part of a broader mitigation strategy that includes protective measures (masking, social distancing, increased hygiene) and contact-tracing and isolation. With 50% or more of infections resulting from pre-symptomatic or asymptomatic transmission, at-home testing may offer an effective option for screening and for breaking chains of transmission. Rapid antigen tests are relatively inexpensive and therefore can be used frequently for detecting infected individuals who are asymptomatic, pre-symptomatic and without known or suspected exposure to SARS-CoV-2¹. However, even with antigen tests, the implementation of community level testing will be challenging, with an impact that is still to be determined².

2.3 RISK/BENEFIT ASSESSMENT

2.3.1 KNOWN POTENTIAL RISKS

Study-related risks include potential loss of confidentiality but steps will be undertaken to minimize this risk. There are no interventions involved in this study.

2.3.2 KNOWN POTENTIAL BENEFITS

The benefit of this study is to learn testing impact on reducing the community spread of the infection, however there is no direct benefit to participants.

3 OBJECTIVES AND ENDPOINTS

Objectives	Outcome Measures	Endpoint
Primary		
1. To assess self-reported social interactions following SARS CoV-2 at-home test result over the study period	Assessments: self-reported data on social distancing, quarantine, social connectedness, healthcare utilization, well-being	Proportion of respondents that report adhering to social distancing guidelines after a test result for the entire study cohort and stratified by participant demographics (e.g., sex) of interest; comparison of proportion adherent after positive vs. negative test result
Secondary		
2. To assess change in self-reported behaviors before and following SARS CoV-2 at-home test result over the study period	Assessments: self-reported data on awareness of the issue, engagement, decisions to act, action, and maintenance	Proportion of respondents that decide to act on precautionary behaviors after a test result for the entire study cohort and stratified by participant demographics (e.g., gender) of interest
3. To assess the impact of at-home testing regimen on self-reported healthcare utilization for SARS CoV-2 treatment	Assessments: self-reported ED visits, hospitalizations, and ICU admission, for SARS CoV-2 evaluation or treatment	Point estimate and 95% confidence interval for each healthcare utilization measure and composite measure for the entire study cohort and stratified by participant demographics (e.g., gender) of interest
4. To assess knowledge of SARS CoV-2 prevention approaches over the study period	Assessments: self-reported data on perceptions and prevention of risks of contracting SARS CoV-2 infection	Proportion of respondents that are knowledgeable of precautionary measures to prevent infection for the entire study cohort and stratified by participant demographics (e.g., gender) of interest
5. Prevalence of positive test result for SARS CoV-2	Assessments: reported results of self-administered SARS CoV-2 antigen test	Prevalence of positive test results with 95% confidence intervals for the entire study cohort and stratified by participant demographic variables of interest

Exploratory		
6. To assess the feasibility of at-home self-administered SARS CoV-2 antigen tests	Assessments: self-reported data on acceptability, practicality, integration, penetration, and demand of at-home self-administered antigen test	Proportion of respondents that find at-home self-administered antigen test acceptable for the entire study cohort and stratified by participant demographics (e.g., gender) of interest
7. To assess participant mobility following SARS CoV-2 at-home test results over the study period	Assessment: mobility patterns as captured by surrogates including activity trackers	Distribution of individual mobility data in response to positive vs. Negative SARS CoV-2 test results.
8. To assess attitudes towards SARS CoV-2 vaccination over the study period	Assessments: self-reported data on perceived susceptibility, severity, benefits, barriers, and cues to action related to SARS CoV-2 vaccination	Distribution of respondent's perception about SARS CoV-2 vaccination for the entire study cohort and stratified by participant demographics (e.g., gender) of interest

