4 STUDY DESIGN

4.1 OVERALL DESIGN

This is an observational, direct-to-participant, nested cohort, sub-study embedded within a public health intervention that distributes at-home, self-administered, SARS-CoV-2 antigen testing kits. Adults and children over 8 years of age living within the pre-identified communities will be included. This sub-study focuses on gathering participant-level data to evaluate behavioral determinants of home testing and socio-behavioral mechanisms of SARS-CoV-2 community transmission.

The smartphone application developed by CareEvolution, called MyDataHelps, will be used for this study, and it is free of charge on Apple or Android devices³. As part of the public health intervention, households will receive test kits and included in them will be information about the app and a QR code to facilitate access. Only after the participants have received information about the public health intervention and received the testing kits, will they be offered the option to participate in this sub-study. Once registered, if the participant wants to be a part of the sub-study, eligibility criteria will be verified and e-consent will be obtained through the app. The smartphone app includes instructions to administer at-home tests, for all participants in the public health intervention. Push notifications will be programmed with messaging to promote adherence including personalization, context, and timing for all participants in the public health intervention. Additionally, participants will have an option to opt-in to reminders for testing 3 times a week at a time of their preference. For participants who provide consent to the sub-study, the app will also feature the ability to report the results of their test results (upload images of test trips), track testing history, respond to surveys and questionnaires, and access study team's contact information. As an alternative to the app, participants can participate in the study via phone interviews conducted by a centralized study call center. Home test kits will include a QR code for the public health intervention app which will link to DCRI call center/eConsent for those interested in participating. Using scripted interview guides, call center staff will be ready to explain study participation, obtain verbal consent, administer study questionnaires including soliciting test results, and issue phone reminders for participants who chose not to use the study app.

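### The primary positive-versus-negative comparison rests on people who completed surveys, and nothing in the plan deals with selective non-response; the resulting bias could go either way.

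*Combined protocol and SAP*

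**What the plan says.** The Synopsis (1.1) and Section 3 define the primary endpoint as "Proportion of respondents that report adhering to social distancing guidelines after a test result", with a "comparison of proportion adherent after positive vs. negative test result". Section 3 also says that it is for the whole cohort.

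The analysis text uses another word. Section 9.4.2 states: "There will be a comparison of the proportion of participants that report adhering to social distancing guidelines after positive vs. negative test result". Section 9.4.1 also refers to participants.

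On the population, Section 9.3 states: "All analyses will be conducted in the PP". One condition for that set is "Complete questionnaires/surveys during the 4 week testing period". A modified set of anyone with at least one home test exists, but only some analyses are repeated in the modified sets.

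On how results arrive, Section 4.1 says that for consented app users "the app will also feature the ability to report the results of their test results (upload images of test trips), track testing history", listed apart from answering surveys. For phone participants, call-centre staff "administer study questionnaires including soliciting test results", so result and behaviour come from the same call.

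Section 4.4 says that whatever data are completed will be analysed. Section 8.1 says that adherence to the survey schedule will be assessed, but not by test result. Section 9 leaves further detail to a separate analysis plan, which is not in the text supplied.

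**The concern.** A survey is answered after the person has seen the result and acted on it, so the decision to answer can depend on both. Someone who did not distance after a positive may be less willing to answer; someone who feels no urgency after a negative may not bother. If these patterns differ between the groups, the difference in reported adherence mixes behaviour with willingness to report it.

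The per-protocol rule builds this selection into the main analysis: a person with a known result who skipped a testing-period survey is removed by definition. The at-least-one-test set would keep that person, but has no rule for the missing outcome.

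At stake is the only comparison in the primary endpoint. The precision table in Section 9.2 gives no protection, because it describes sampling error alone.

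**Working it through.** **The plan's own figure.** Section 9.2 tabulates a margin of 1.37% for a 50% proportion at N = 5,000. The simple formula gives 1.96 × √(0.5 × 0.5 / 5,000) = 1.386%. Multiplying by √((300,000 − 5,000)/299,999), with the maximum cohort taken as a finite population (an inference), gives 1.374%. The figure reproduces. It is the margin for one proportion with complete response.

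**Formula.** Let p be true adherence in a group, and a and n the response probabilities of adherent and non-adherent people. The proportion among respondents is

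p·a / (p·a + (1 − p)·n).

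All values of p, a and n below are assumptions, apart from the 50% that Section 9.2 uses as an illustration.

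**Case A: selective response in positives only.** True adherence is 70% after a positive and 60% after a negative (gap 10). Adherent positives answer at 70%; response in negatives is unrelated to adherence.

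| Non-adherent positives who answer | Observed in positives | Observed gap |
|---|---|---|
| 60% | 0.49/(0.49 + 0.180) = 73.1% | 13.1 |
| 45% | 0.49/(0.49 + 0.135) = 78.4% | 18.4 |
| 35% | 0.49/(0.49 + 0.105) = 82.4% | 22.4 |

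**Case B: equal selectivity.** True adherence is 60% and 50% (gap 10); in both groups 80% of adherent and 60% of non-adherent people answer. Positives: 0.48/(0.48 + 0.24) = 66.7%. Negatives: 0.40/(0.40 + 0.30) = 57.1%. Observed gap 9.5.

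**Case C: negatives more selective.** As B, but 40% of non-adherent negatives answer. Negatives: 0.40/(0.40 + 0.20) = 66.7%. Observed gap 0.

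**Case D: positives truly less adherent.** True adherence is 40% and 50% (gap −10), with 80%/60% response in positives only. Positives: 0.32/(0.32 + 0.36) = 47.1%. Observed gap −2.9, so the difference shrinks.

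**Case E: no true difference.** Both groups are at 50%, adherent positives answer at 80%, and negatives answer at 80% whatever they did. If non-adherent positives answer at 70%, 60%, 50% or 40%, the false gap is 3.3, 7.1, 11.5 or 16.7 points. Even a 10% relative shortfall in their response gives 0.5/(0.5 + 0.45) − 0.5 = 2.6 points, about twice 1.37.

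**The denominator word.** Take case E at 60% and count everyone with a known result, so that non-responders count as not reporting adherence. Positives are then 0.5 × 0.8 = 40% and negatives 0.5 × 0.8 = 40%: gap 0, against 7.1 among respondents. The two words can give different answers from the same data. Neither is safe in general, since the second treats every non-responder as non-adherent. Within the per-protocol set the two words coincide for testing-period surveys; they part in the at-least-one-test set and at later surveys.

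**Bounds.** In the same case, positives respond at 0.5 × 0.8 + 0.5 × 0.6 = 70%. Worst-case limits are 0.571 × 0.70 = 40% to 40% + 30% = 70%. For negatives (80% response) they are 40% to 60%. The gap lies between 40 − 60 = −20 and 70 − 40 = +30, which includes the true 0.

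**Does a 10 to 30 point shift cover these cases?** In case A, adherence among non-responding positives is 0.21/(0.21 + 0.12) = 63.6%, 0.21/(0.21 + 0.165) = 56.0% and 0.21/(0.21 + 0.195) = 51.9%. These are 9.5, 22.4 and 30.5 points below the observed values, so the range roughly spans case A. The most extreme version of case E needs 66.7 − 0.10/(0.10 + 0.30) × 100 = 41.7 points, which only the bounds cover.

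**The case against.** The study is described as mainly descriptive with an exploratory hypothesis (9.1), and detail is deferred to a separate analysis plan. Non-response is worked against in practice through reminders (6.4), call-centre contact with non-completers (7.3) and payment of up to $50 for completing all surveys (5.5). Mobility data by test result (Section 3, exploratory) need not depend on survey answers. The mixed models in 9.4.1 would use each person's other answers.

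Much of this is fair, and it keeps the point below the level of a fatal flaw. But reminders and payment may reduce non-response without showing whether the remainder is selective. A descriptive proportion is distorted in the same way as a tested one. Mixed models address correlation within participants and households; they cannot repair non-response that depends on the unreported behaviour, and people excluded from the per-protocol set contribute nothing. Deferral to another document is not yet a rule.

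Four stronger readings are tempting, and the documents do not support them:

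- *The gap is inflated.* This needs response to be more selective in positives, and positives to be truly no less adherent. Cases B, C and D show otherwise.
- *The app already holds the non-responders' results.* It holds them only for app users who chose to report. A missed phone call loses both result and outcome.
- *Section 9.4.2 itself restricts the analysis to respondents.* It says participants. The restriction comes from the endpoint wording and the per-protocol rule.
- *A small positive group is more exposed.* This bias does not depend on group size, and the plan states no expected prevalence.

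**Conclusion.** The point stands in this form: the primary comparison is conditional on survey completion, through both the endpoint wording and the per-protocol definition; the denominator is worded inconsistently; and the text supplied has no method for selective non-response. The direction of any bias is unknown. Under the assumed rates, a true 10-point gap can show as anything from 0 to about 22 points, and a true gap of zero as up to 16.7. These are illustrations, not forecasts, because the documents give no response rates by result. The plan should be changed, and this can be done with data it already collects.

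**What to change.** 1. Use one denominator term in 1.1, 3, 9.4.1 and 9.4.2.
2. In 9.4.2, repeat the primary comparison in the at-least-one-test population of 9.3. Link each reported result to the next scheduled social-interactions survey (after Baseline: Weeks 1, 3, 5, 13 and 21), and report survey response after positive and after negative results. No such survey is scheduled in Weeks 2 or 4, so without a linking rule refusal is confused with no survey being due. The rule must fit the note in 1.3 that questionnaires may be completed in the week following a test. It must also say what happens when several results precede one survey: three tests a week over two weeks can give six.
3. In that set, give an estimate weighted by the inverse probability of response, using result, Baseline social interactions, earlier answers, age, sex and app or phone route.
4. Add a shift analysis that varies non-responders' adherence separately in positives and negatives, lower and higher (for example by 10 to 30 points), or show worst-case bounds. For a group with response rate r and shift δ, the adjusted proportion is the observed proportion + (1 − r)·δ.

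The cost is analysis-plan wording and a small amount of extra analysis, with no new data collection. Weights correct only for measured predictors, which is why step 4 is needed too. App users who reported no result and phone participants who missed a call have unknown results and must be shown as such.
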